4.2.3. Change from a Reference Point

For Period 1 and Entire Study analyses, the change from baseline at a post-baseline visit will be derived as:

```
Change = (Score at the Post-Baseline Visit) – (Baseline Score)
```

For Period 2 analyses, change from Month 12 will be the change used in the analyses.

4.3. Efficacy-Related Definitions

4.3.1. SANDE Global Score

The SANDE global score will be calculated using the following formula:

```
SANDE Global Score = \sqrt{\text{(Frequency of symptom score)}} \times \text{(Severity of symptom score)}
```

If frequency or severity will be missing for a subject at the same visit, the SANDE global score will be missing.

4.3.2. Dry Eye symptoms-related Quality of Life Score (DEQS)

Dry Eye related Quality of life Score (DEQS) consists of 15 items related to dry eye symptoms and influence on daily life. The overall degree of Quality of Life impairment is calculated as a summary score (0 to 100).

The DEQS includes two subscales, which first assess the *frequency* of the symptoms and disability (0 to 4) and then assess symptom *degree* (1 to 4).

The DEQS **overall** *frequency* **of impairment score** will be calculated with the following formula (Inomata et al., 2020; Sakane et al., 2013):

$$score \ = \frac{(sum \ of \ the \ Frequency \ scores \ of \ all \ questions \ answered) \times 25}{total \ number \ of \ questions \ answered}$$

The DEQS **overall** *degree* **of impairment score** will be calculated by the following steps:

- 1. For all questions with the *frequency* score (Column A) 0, set the *degree* score (Column B) to 0.
- 2. Calculate overall *degree* score with the formula:

```
score = \frac{\text{(sum of the Degree scores for all questions answered)} \times 25}{\text{total number of questions answered}}
```

The summary scores range from 0 to 100, with a higher score representing greater disability.

4.3.3. Conjunctival Fluorescein Staining Total Score

Conjunctival fluorescein staining total score will be the sum of conjunctival fluorescein staining score from nasal and temporal sides.

4.3.4. Markedly Improved Status

Markedly improved patients are defined for the Period 1 portion of study. The markedly improved status is defined as:

- If a subject's study eye had CFS score of 3 or 4 at Baseline, the improvement in CFS score at a post-baseline visit has to be 2 or more on the modified Oxford scale.
- If a subject's study eye had a CFS score of 5 at Baseline, the improvement in CFS score at a post-baseline visit has to be 3 grades or more on the modified Oxford scale.

4.3.5. Relapse Status

For this study, the relapse status is defined as an increase of CFS score of 2 or more on the modified Oxford scale (compared to CFS score at Month 12) during Period 2.

4.4. Safety-Related Definitions

4.4.1. Adverse Event

Under the Protocol NVG14L127, an adverse event is any untoward medical occurrence in a clinical investigation subject administered a study drug. An AE does not necessarily have a causal relationship with the study drug. For this study, the study drugs are IKERVIS® and Vehicle. Regardless of causality to the study treatment, an AE can be an unintended sign (including an abnormal laboratory finding), symptom, or disease temporally associated with the use of study treatment.

An *on-study* AE can occur any time after the date of informed consent through the last study visit. An AE will be considered as *treatment-emergent* if the onset date of the AE occurred on or after the treatment start date of the analysis period. Treatment-emergent AEs (TEAEs) are a subset of on-study AEs. Both on-study and TEAEs will be collected, but only TEAEs will be tabulated.

The severity of each AE will be graded by the Clinical Investigator as Mild, Moderate, or Severe. AEs will be rated by the Investigator as to their causality/relationship to the study drug.

Each AE will be classified into a system organ class (SOC) and coded to a preferred term (PT) using Medical Dictionary for Regulatory Activities (MedDRA), version 23.1 published in 2020.

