#### 9.5. Administration

The investigational product will be instilled once daily into the affected eye(s), at bedtime.

The study medication and sponsor provided unpreserved artificial tears are to be dispensed only by the investigator or his/her designee, and will be used in accordance with this protocol.

Under no circumstances will the investigator allow the study products to be used other than directed by the protocol. All dispensations and returns of study medication have to be documented in the investigator's file provided by the Sponsor.

In order to ensure patient anonymity, patients will be identified by codes or other means of record identification.

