#### 13.6.1. Adverse Events

An adverse event is treatment emergent if it occurs or worsens after the first dose of study treatment.

Adverse events will be coded using the MedDRA dictionary. Frequencies and percentages will be given as follows: 1) Overall summary; 2) by system organ class and preferred term, 3) by system organ class, preferred term and maximal severity, 4) by system organ class, preferred term and relationship to study medication and study procedure, respectively, and 5) by system organ class, preferred term, maximal severity, and relationship to study medication and study procedure, respectively.

Separate analyses will be performed for AEs and SAEs, and for ocular and systemic AEs and SAEs, respectively. Ocular AEs will be summarized for the analysis eye and the fellow eye separately.

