4.1.2. Treatment Start Date and End Date

The treatment start and end dates for each treatment period and the study are defined as follows:

Treatment Period	Treatment Start Date	Treatment End Date
Open-Label Treatment Period (Period 1)	The date of the first dose of the open-label IKERVIS treatment (or Day 1 date)	 The date of the last dose of the open-label IKERVIS treatment The date of the day before the Month 12 Visit will be considered the Period 1 treatment end date for subjects who completed Period 1 treatment. The date of the day before the Exit Visit will be used for subjects who prematurely discontinued from the study. If the Exit Visit date of a non-completer is not available, then the day before the last available visit date will be considered the treatment end date.
Double-Masked Treatment Period (Period 2)	The date of the first dose of the double-masked study treatment (or Month 12 Visit date)	 The date of the last dose of the double-masked study treatment The date of the day before the Month 36 Visit will be considered the Period 2 treatment end date for subjects who completed the study. The date of the day before the Exit Visit will be used for subjects who prematurely discontinued from the study. If the Exit Visit date of a non-completer is not available, then the day before the last available visit date will be considered the treatment end date.

For each treatment period, the treatment end date will be set to missing if the treatment start date is missing.

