5.5. Interim Analysis

There is one interim analysis planned for this study. The purpose of the interim analysis is to present appropriate summary of data collected for the period 1. Interim analysis will be conducted once all subjects will have completed their Month 12 Visit or withdrawal visit.

Data cut criteria for this interim analysis is shown in Table 3.

Table 3 Data Cut Plan for Interim Analysis

Analysis Data	Data Example	Data Cut Criteria
Visit Data	IOP, TBUT, DEQS, etc. that are collected on visit date	Data collected at Month 12 or earlier will be included.
Non-visit Data	AE, medication, procedures, CSI, etc.	Incidents that happened up to the day of the first dose in Period 2 study drug will be included in the analysis.

Since the first 12 months of the study will be open-label study, no adjustment of alpha level and no Data Monitoring Committee will be needed for this study.

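### Adverse events with onset on the Month 12 visit day can count in both Period 1 and Period 2, although the first masked dose is at bedtime, and the SAP drops the protocol's worsening clause without listing the change

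*SAP*

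**What the plan says.** **Treatment-emergence rule.** SAP 4.4.1 counts an event "if the onset date of the AE occurred on or after the treatment start date of the analysis period". It sets no end date for either period and has no worsening limb. It adds that only treatment-emergent events are tabulated.

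**Start of Period 2.** SAP 4.1.2 gives "The date of the first dose of the double-masked study treatment (or Month 12 Visit date", so two start dates are possible. For completers of Period 1 the same table says: "The date of the day before the Month 12 Visit will be considered the Period 1 treatment end date".

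**Time of dosing.** Protocol 9.5: "The investigational product will be instilled once daily into the affected eye(s), at bedtime".

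**Other SAP rules for the same day.** In the analysis windows of SAP 4.1.4, Period 2 Day 1 belongs to Month 12, which is the reference for Period 2. For adverse events, the Period 1 interim cut in SAP 5.5 reads: "Incidents that happened up to the day of the first dose in Period 2 study drug will be included in the analysis".

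**Worsening.** Protocol 13.6.1 states: "An adverse event is treatment emergent if it occurs or worsens after the first dose of study treatment". The synopsis says the same. SAP Section 10, which lists changes to the protocol's analyses, does not mention the difference.

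**The concern.** Month 12 is where open-label IKERVIS ends and the randomised comparison begins. It is also a full examination day, with adverse events, visual acuity, slit lamp, staining and intraocular pressure all assessed. An event dated to that day before the bedtime dose arose under open-label drug, whichever arm the patient was then assigned to. Booking it to Period 2 attributes it to a masked treatment that had not been given.

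This can reach the primary safety endpoint. Loss of visual acuity is one of the four ocular surface complications, and SAP 9.1 compares the arms on time to first complication in Period 2. A pre-dose event on Period 2 Day 1 would also use up that patient's first event, so a later event under masked treatment would not count.

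The missing worsening clause matters because one arm moves from active drug to vehicle. An event that was ongoing at Month 12 and worsens afterwards is of interest in that comparison, but its onset date stays in Period 1.

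**Working it through.** The plan states no figure on this point, so there is none to reproduce. The check is of dates and rules, followed by an illustration of size.

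**1. Order of events on the day.** Protocol 10.1 asks for assessments in the listed order. In 10.1.3, adverse events, acuity, slit lamp, staining and intraocular pressure come before randomisation and dispensing. The first masked dose then follows at bedtime. The adverse event items in Protocol 12.2.4.1 include an onset date but no onset time, so the date alone decides the period.

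**2. Date test.** Take the Month 12 visit as Day 360. The tests are: Period 2 event if onset ≥ Period 2 start; Period 1 event if onset ≥ Day 1; inside the interim cut if onset ≤ first masked dose date.

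| First masked dose | Period 2 start taken as | Onset | Period 2 event | Period 1 event (4.4.1 as written) | In interim cut |
|---|---|---|---|---|---|
| Day 360 | either date | Day 359 | no | yes | yes |
| Day 360 | either date | Day 360 | yes | yes | yes |
| Day 360 | either date | Day 361 | yes | yes | no |
| Day 361 | first dose date | Day 360 | no | yes | yes |
| Day 361 | visit date | Day 360 | yes | yes | yes |

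A visit-day onset is counted in both periods when the first dose is that day. If the first dose is a day later, the answer depends on which start date is used. A Day 361 onset still meets the Period 1 rule as written; only the interim cut removes it when the first dose was on Day 360.

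**3. The SAP's other rules.** The end date in 4.1.2 puts the visit day outside Period 1 treatment. The windows in 4.1.4 make it the pre-treatment reference. The cut in 5.5 puts its events in Period 1. The rule in 4.4.1 puts them in both periods. These cannot all hold.

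**4. Complication intervals.** SAP 9.1 tabulates Months 1-12, 13-24, 25-36 and 13-36 without day bounds. With 30-day months, Month 12 ends on Day 12 × 30 = 360, so a Day 360 onset would fall in Months 1-12. But the visit may take place from Day 353 to Day 367. For a visit on Day 365, a pre-dose onset that day would fall in Month 13. For a visit on Day 355, masked-treatment onsets on Days 356 to 360 would fall in Months 1-12.

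**5. Size, by assumption only.** Let q be the share of randomised patients with a pre-dose visit-day event, equal in both arms because it precedes masked exposure. An arm with true risk p then shows 1 − (1 − p)(1 − q). With the planned 147 and 98 patients, and q from 0.5% to 3% (assumed):

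- Events added: 147 × 0.005 = 0.7 to 147 × 0.03 = 4.4 on IKERVIS; 98 × 0.005 = 0.5 to 98 × 0.03 = 2.9 on vehicle.
- Assumed true risks 3% and 6%: the odds ratio is (0.03/0.97)/(0.06/0.94) = 0.485. At q = 0.5% the risks become 3.49% and 6.47%, odds ratio 0.52. At q = 3% they become 5.91% and 8.82%, odds ratio 0.65.
- The risk difference is multiplied by 1 − q: from 3.00 to 8.82 − 5.91 = 2.91 percentage points at q = 3%.
- Assumed equal risks of 4%: the odds ratio stays at 1.0 for every q.

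**6. Worsening.** Protocol 12.1.3 has clinically significant change in concomitant disease reported as an adverse event. Protocol 12.2.1.1 says worsening of a pre-existing condition may be one. Neither says that worsening of an ongoing adverse event opens a new record, and the items in 12.2.4.1 include no worsening date.

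**The case against.** **The route is narrow.** The rule uses onset date, and Protocol 12.2.4.1 records the site's awareness date separately. An event found at Month 12 that began earlier stays out of Period 2. Randomised patients have just shown marked corneal improvement, so a staining event in the study eye that day is unlikely. This stands: only onsets dated to the visit day are affected.

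**The main complication tables may already exclude it.** Read by 30-day months, Day 360 lies in Months 1-12, and SAP 4.4.1.1.4 provides for a data review meeting. This stands in part. The intervals have no day bounds, actual visits vary around Day 360, and the calendar reading does not settle the by-arm adverse event tables or the Cox model.

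**The convention is ordinary.** Counting onsets on or after the start date is usual when times are not collected, and within one table SAP 9.2 counts a patient once per term. Both are fair. The double counting is across the period tables, and the weakness is in using an open-ended rule at the boundary between open-label and randomised treatment.

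**Three stronger readings do not hold.** A reader might infer a share of misattributed events from the visit schedule. Month 12 is one of nine visit days from Month 12 to Month 36, but one of five with acuity and slit lamp. Neither fraction is a documented share of onsets, and nothing supports an even spread. A reader might infer that worsening is lost altogether. It is not: part can enter as new events under Protocol 12.1.3 and 12.2.1.1, and SAP 9.2 lists non-treatment-emergent events. The protocol's own clause is also tied to the first dose of study treatment, not the first masked dose, so it never gave a Period 2 worsening rule. Finally, a reader might infer that the arms are always pulled together. For visit-day events that is true of a ratio only if the true risks differ; for worsening it would require more worsening on vehicle, which the documents do not establish.

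**Conclusion.** The SAP handles the Month 12 visit day inconsistently, and the treatment-emergence rule should be corrected. As written, a pre-dose visit-day onset becomes a Period 2 event when the first masked dose is that day or the visit date is used as the start. It also counts in Period 1, as on the literal text do later Period 2 events. It can therefore enter the by-arm Period 2 tables and the time-to-first-complication analysis.

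The effect is expected to be small and proportional to allocation. It inflates both arms' rates, does not favour one arm, and dilutes a ratio only where true risks differ. Its size cannot be taken from the documents; the odds-ratio shifts shown rest on assumed risks and an assumed share of visit-day events.

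The unlisted omission of the worsening clause is a separate and limited gap. It concerns an event that began in Period 1 and worsens under masked treatment without a new record.

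**What to change.** - Define Period 2 treatment-emergent events as those with onset after the Month 12 visit date, or after the first masked dose date if that is later. Assign visit-day onsets to Period 1 unless they are documented as occurring after the first masked dose.
- End Period 1 treatment-emergent events at that same date.
- Use the same day boundary for the Month 1-12 and Month 13-24 complication intervals and for the Cox model in SAP 9.1.
- Restore the worsening clause, with worsening of an ongoing event after the first masked dose recorded as a new event with its own onset date. Otherwise, list and justify the omission in Section 10.

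The date rules cost a few lines of SAP wording. The worsening rule also needs a recording instruction to sites, since the protocol's list of adverse event items has no worsening date; where that is no longer practical, the Section 10 entry is the workable option. The downside is that a rare true same-night event, if not documented as such, falls in Period 1.

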1. INTRODUCTION

This statistical analysis plan (SAP) specifies the statistical methods and analyses to be implemented for the data collected from the IKERVIS PAES study within the scope of Santen's Protocol NVG14L127, "A phase IIIb, prospective, interventional, multicentre, three-year study to explore the long-term evolution of sign and symptoms, and occurrence of complications in dry eye disease subjects with severe keratitis receiving IKERVIS® (1mg/ml ciclosporin) eye drops". It applies to the study protocol Amendment 1 (version 3.0), dated 17-OCT-2018, and provides detailed instructions as to how each analysis will be performed.

Results obtained from the analyses specified in the final approved version of the SAP will become the basis of the clinical study report (CSR) for this protocol. Deviations from the final approved version of the SAP must be substantiated by sound statistical reasoning and documented in the CSR.

REVISION HISTORY FROM THE PREVIOUS VERSION (1.0):

- Reflected the latest version of MedDRA (Sec. 4.4)
- Updated the definitions of ocular surface complication (Sec. 4.4.1.1)
- Updated analysis set (Sec. 6)
- Added Sjogren patient population summary (Sec. 7 and 8)
- Added medical history summary for period 2 (Sec. 7.5)
- Added CFS shift table (Sec. 8.2)
- Added CFS complete resolution summary (CFS=0 at post BL) (Sec. 8.2)
- Added MMRM to estimate treatment difference for secondary endpoints (Sec. 8.2) and updated related section (Sec. 5.1 and 5.4)
- Clarified the duration of detail for ocular surface complication (Sec. 9.1)
- Added SAS sample code (Sec. 12)

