- Best Corrected Distance Visual Acuity (BCDVA) and change from baseline at Month 6, Month 12, Month 24 and Month 36 visits
- Incidence and severity of ocular and systemic adverse events (AEs) over the three-year study period.

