9.2. Adverse Event

Subjects with any AE(s) will be tabulated by type of AE(s) by study period and for each actual treatment received and overall (Period 2 and Entire Study) for all AEs, ocular AEs, and non-ocular AEs separately. Unless otherwise specified, any AE experienced by either eye or both eyes will be counted once for that AE. In addition to the overall AE summary, subjects with any AE(s) will be tabulated by SOC and preferred term. A subject who experienced multiple AEs within a SOC or preferred term will be counted only once for that SOC or preferred term. SAEs, ADRs, serious ADRs will be tabulated similarly. Non-serious AEs (including number of events) and CSIs will also be summarized by SOC and preferred term.

AEs, SAEs, ADRs, serious ADRs, ocular AEs, AEs leading to death, AEs leading to study drug discontinuation, non-TEAEs, and CSIs, if any, will be listed separately.

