10. CHANGES TO THE PROTOCOL-SPECIFIED ANALYSES

10.1. The Term "Study Eye"

The terms "analysis eye" and "study eye" were used interchangeably throughout the protocol. In this SAP the term "study eye" will be used throughout.

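### AE severity is half of a named safety endpoint, yet SAP 9.2 drops the protocol's table by maximal severity and SAP 10 does not log the omission

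*SAP*

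**What the plan says.** SAP 2.2.2 lists as a safety endpoint "Incidence and severity of ocular and systemic adverse events (AEs) over the three-year study period", and Protocol 5.3.2.3 has the same endpoint. The grade is collected. SAP 4.4.1 states: "The severity of each AE will be graded by the Clinical Investigator as Mild, Moderate, or Severe".

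Protocol 13.6.1 plans five AE summaries. The third is "by system organ class, preferred term and maximal severity", and the fifth crosses the same breakdown with relationship to study medication and to study procedure.

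SAP 9.2 says: "In addition to the overall AE summary, subjects with any AE(s) will be tabulated by SOC and preferred term". SAEs, adverse drug reactions (ADRs) and serious ADRs follow the same layout, and non-serious AEs and cases of special interest are also shown by SOC and PT. Several listings follow. Severity is not mentioned in that section.

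On treatment emergence, Protocol 13.6.1 says: "An adverse event is treatment emergent if it occurs or worsens after the first dose of study treatment". SAP 4.4.1 counts an AE as treatment-emergent "if the onset date of the AE occurred on or after the treatment start date of the analysis period", and adds that only treatment-emergent AEs (TEAEs) are tabulated.

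SAP 10, headed "CHANGES TO THE PROTOCOL-SPECIFIED ANALYSES", covers the study-eye term, the efficacy endpoint wording, the interim analysis and the population definitions. It mentions neither the AE tables nor the TEAE definition. The revision history in SAP 1 mentions neither as well.

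**The concern.** Protocol 13.1 leaves the detail of all analyses to the SAP, and SAP 1 makes the SAP-specified analyses the basis of the study report. A reporting team that follows SAP 9.2 will tabulate how many patients had each event, but not how bad the events were.

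That matters for this drug. Its main known tolerability problem is instillation site pain, and the clinical weight of that depends on grade. An any-grade rate cannot distinguish a brief mild sting from pain that interferes with normal activities. The secondary objective of describing safety and tolerability over three years would then be met for incidence, with no planned summary for severity.

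The narrower TEAE definition raises a second question: whether events that worsen, rather than start, on treatment drop out of the tables.

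**Working it through.** The main check compares the texts. The arithmetic only illustrates what a severity table would add.

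**Step 1. Planned AE tables**

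| Item | Protocol 13.6.1 | SAP 9.2 |
|---|---|---|
| Overall summary | yes | yes, contents not itemised |
| SOC and PT | yes | yes |
| SOC, PT and maximal severity | yes | not specified |
| SOC, PT and relationship to study drug | yes | covered by the ADR tables |
| SOC, PT, maximal severity and relationship | yes | not specified |

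Both protocol tables that carry severity are absent from the SAP. The endpoint that needs them is unchanged.

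**Step 2. Why grade matters (pivotal study, Protocol 4.1.1, instillation site pain)**

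| Grade | IKERVIS | Vehicle | Difference |
|---|---|---|---|
| Any | 29.2% | 8.9% | 20.3 points |
| Mild | 16.9% | 4.4% | 12.5 points |
| Moderate | 8.4% | 2.2% | 6.2 points |
| Severe | 3.9% | 2.2% | 1.7 points |

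The grade differences sum to 12.5 + 6.2 + 1.7 = 20.4, which differs from 20.3 by rounding. The mild share of the excess is 12.5/20.4 = 61%. For moderate or severe pain the rates are 8.4 + 3.9 = 12.3% and 2.2 + 2.2 = 4.4%, a difference of 7.9 points.

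**Step 3. Would the table be informative?** Assume, for illustration only, that the pivotal IKERVIS rates held in 350 Period 1 patients. The SOC and PT table would show 0.292 × 350 = 102 patients with pain. It would not show that 0.169 × 350 = 59 were mild, 0.084 × 350 = 29 moderate and 0.039 × 350 = 14 severe. The 95% half-width for moderate or severe pain would be 1.96 × √(0.123 × 0.877/350) = 3.4 points.

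For Period 2, with the planned 147 and 98 patients, the documents give no usable rate. At an assumed 4% versus 2%, the half-width of the difference is 1.96 × √(0.04 × 0.96/147 + 0.02 × 0.98/98) = 4.2 points.

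**Step 4. What the loss of worsening does**

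- *Measured against the protocol.* The protocol's anchor is the first dose of study treatment, which is the open-label dose on Day 1. Only AEs that start before that dose are affected. Protocol 10.1.1 puts consent, baseline examinations and dispensing at one visit, and the SAP counts onsets on the start date itself. Almost nothing is lost.
- *Within the SAP's own period rule.* An AE that starts in Period 1 and worsens on masked treatment has an onset before the Period 2 start, so it is not a Period 2 TEAE unless the worsening is entered as a new AE. Protocol 12.1.3 directs that clinically significant changes in concomitant disease be reported as AEs. Protocol 12.2.1.1 treats a significant change from baseline as an AE, except for continuation of a documented pre-existing condition. These largely direct a new record, with its own onset date. Either way, the original event still counts in the Period 1 tables and, for a randomised patient, in the entire-study tables.
- *Size.* The documents do not say how many AEs are ongoing at Month 12 or later worsen. For instillation site pain alone, take 13.0% (extension study) to 29.2% (pivotal study) ever reporting it. Assume that 10% to 50% of those are ongoing and that 0 to 20% of those worsen. The upper end is 0.292 × 0.50 × 0.20 = 2.9%, which is 4.3 of 147 and 2.9 of 98 patients. The lower end is zero. Any worsening recorded as a new AE reduces these counts further.

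**The case against.** The best defence is that severity is not lost. AEs, ocular AEs and ADRs are listed under SAP 9.2. SAP 5 lists individual data, says that all measures are summarised, and allows additional analyses documented in the study report. The overall AE summary and the AE types are not itemised and could include grade. SAEs and serious ADRs are tabulated and AEs leading to discontinuation are listed, so the gravest harm is visible. The endpoint is secondary and descriptive in an exploratory study, and the table could be produced at reporting.

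Most of this stands, and it sets the weight of the point. A reader might infer that severity will go unreported, but the documents do not support that. What the defence does not supply is a rate by grade, by period and by arm. A listing gives no rate, an un-itemised summary is not a commitment, and even an overall count by grade would not replace the SOC and PT breakdown that the protocol plans.

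A reader might also infer that the SAP removed a protocol rule for worsening on masked treatment, or that the Period 2 comparison is biased. Neither follows. The protocol has no rule tied to the first masked dose, and both arms are counted from the same starting point.

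The pivotal-study illustration has limits as well. Period 1 has no vehicle arm, so it cannot show an excess. Period 2 patients have already used the drug for a year and improved, so the pivotal rates do not predict what they will report.

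**Conclusion.** The point holds for the severity table. A protocol-planned summary of half of a named endpoint has no specified tabulated result, and the omission is not logged. It should be corrected, but no primary conclusion depends on it and the incidence half of the endpoint is sound.

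The TEAE wording is a minor inconsistency. Its effect is close to nil against the protocol and, within Period 2, at most a handful of patients under the assumed ranges above, possibly none.

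This rests on the supplied text. The SAP 12 appendix is not shown, and the revision history describes the addition there only as SAS sample code.

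**What to change.** **SAP 9.2.** Add TEAEs by SOC, PT and maximal severity, for all AEs and for ocular AEs: in Period 1, in Period 2 by actual treatment received, and for the entire study. If the sponsor means to omit the table, say so with the reason in SAP 10.

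**SAP 4.4.1.** Either restore worsening to the definition, or keep the onset rule, list by arm the AEs ongoing at the first masked dose with their severity, and log the change in SAP 10.

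**Cost.** Severity is already graded for every AE, so the main change is one table layout repeated by period and a few lines of text. The price is more small cells at PT level. Restoring worsening period by period costs somewhat more. The AE items in Protocol 12.2.4.1 include one severity entry and no date of change, so records ongoing at Month 12 would need checking, and one event could count in both periods. The listing option avoids both.
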